6.3. Safety Set

Safety analyses will be performed on the Safety Set defined as all patients who receive at least 1 dose of study drug.

6.4. Other Sets

Not applicable.

7. STATISTICAL ANALYSIS

All analyses will be performed using Statistical Analysis Software[®] (SAS[®]) release, version 9.4 or higher (SAS Institute Inc., Cary, NC, USA) or other validated statistical software. Continuous variables will be summarized using descriptive statistics, including number of observations, mean, standard deviation (SD), median, minimum, and maximum values. Categorical variables will be summarized by frequency counts and percentage.

7.1. Study Patients

7.1.1. Disposition of Patients

All patients will be included in the summaries of patient disposition, which will describe the frequency and percentage of patients enrolled and treated and who completed or withdrew from the study, along with reason for withdrawal from the study. The number and percentage of patients who are treated, discontinue treatment (along with reason for treatment discontinuation), complete or withdraw from the Initial Evaluation Period (along with reason for withdrawal), enter the Extension Period, and complete or withdraw from the Extension Period (along with reason for withdrawal) will be tabulated.

7.1.2. Protocol Deviations

Important protocol deviations will be determined per the standard operating procedure (SOP) “Identification, Handling, and Documentation of Protocol Deviations” (SOP-G-CL-0044). The number and percent of patients with specific protocol deviations will be summarized for all enrolled patients by major and minor deviations.

To ensure completeness of the list of important protocol deviations, the following will be identified programmatically from the database:

1. Patients from whom informed consent was not obtained
2. Patients who violated any inclusion/exclusion criteria
3. Patients who took prohibited medications or underwent any prohibited procedure
4. Patients who received less than 100% of the protocol specified number of doses of study drug during the Initial Evaluation Period
5. Patients found not to satisfy one or more of the following inclusion/exclusion criteria (Inclusion Criterion number 2c or Exclusion Criteria numbers 1 and 2) whom are not discontinued from the study.

A by-patient listing of inclusion/exclusion criteria, as well as protocol deviations will be presented, separately.

7.1.3. Demographics, Disease Characteristics, and History

Patient demographic and baseline characteristics, including medical history and transplant history, will be summarized for the FAS and Safety Set.

7.1.3.1. Demographics

The following demographic variables will be summarized:

- Gender
- Race
- Age (years) at first Infusion
- Weight at first Infusion
- Height at first Infusion

A by-patient listing of demographics will be generated.

7.1.3.2. Disease Characteristics

The following disease characteristics will be summarized:

- Age at first aHUS symptoms
- Pretreatment extra-renal signs or symptoms of aHUS
- A disintegrin and metalloproteinase with a thrombospondin type 1 motif, member 13 (ADAMTS-13) activity

A table summarizing pretreatment extra-renal signs or symptoms of aHUS will also be presented.

A by-patient listing of disease characteristics will be generated.

7.1.3.3. Medical History and Baseline Physical Examination

Medical history will be summarized by number and percentage of patients within each Body System. Patients will be counted only once at the Body System level.

A separate table summarizing history of emergency room visits and hospitalizations due to aHUS, a table summarizing kidney transplant history, as well as a table presenting baseline physical examination results will also be generated.

By-patient listings of these data will be generated.

7.1.4. Prior and Concomitant Medications / Nonpharmacologic Procedures

Prior and concomitant medications (including vitamins and herbal preparations) will be coded using the World Health Organization Drug Dictionary (WHO-DRUG), while prior and concomitant nonpharmacologic therapies and procedures (any therapeutic intervention, such as surgery/biopsy or physical therapy) will be coded using MedDRA.

Prior medications or procedures are defined as any non-study medications or procedures that were started, and were stopped, prior to the date of first infusion. Concomitant medications or procedures are defined as any non-study medications or procedures that were taken or occurred while the patient also received study medication. Prior and concomitant summaries will be presented separately.

Medications will be summarized by Anatomic-Therapeutic-Chemical (ATC) level 4 class and preferred drug name using frequency counts and percentages of patients for the Safety Set. Procedures will be summarized similarly, but by MedDRA Class and preferred term.

A table summarizing pretreatment plasma exchanges and plasma infusion as well as kidney dialysis will be generated. A similar table will summarize concomitant kidney dialysis.

In the event a patient receives a prohibited medication or undergoes a prohibited procedure, this will be reported as a protocol deviation as described in [Section 7.1.2](#).

By-patient listings of these data will be provided separately.

7.2. Efficacy Analyses

The FAS is the primary analysis set for all efficacy analyses. The primary analysis and selected secondary efficacy analyses will be repeated on the PPS as sensitivity analyses.

7.2.1. Primary Analysis

The primary efficacy endpoint is Complete TMA Response during the 26-week Initial Evaluation Period. The primary analysis will consist in estimating the proportion of complete TMA responders among ALXN1210 treated patients. This will be performed by calculating the point estimate and a 2-sided 95% confidence interval (CI) for the proportion of complete TMA responders in ALXN1210 treated patients, where the numerator will be the number of patients achieving complete TMA response during the 26-week Initial Evaluation Period and the denominator will be the number of patients in the FAS. The CI will be based on the asymptotic Gaussian approximation method with a continuity correction.

The criteria for Complete TMA response are presented in [Section 5.1.1](#). Patients must meet all Complete TMA Response criteria at 2 separate assessments obtained at least 4 weeks (28 days) apart, and any measurement in between. To be considered a responder during the 26-week Initial Evaluation Period, the latest time point a patient can first meet the response criteria is 28 days before the Day 183 assessment.

Formal statistical comparison analyses are not planned for this estimation study. Results from ALXN1210 treated patients will be evaluated in the context of results observed in patients treated with eculizumab in prospective eculizumab studies.

7.2.1.1. Handling of Dropouts or Missing Data

For evaluation of Complete TMA Response during the 26-week Initial Evaluation Period (primary endpoint), patients missing an efficacy assessment that is part of the definition of Complete TMA Response while still on-study, will have their last observation carried forward (LOCF). For patients who will have discontinued from the study prior to Week 26, their data up to the time of discontinuation will be used to assess Complete TMA Response. A confirmatory result cannot be from an assessment that was carried forward from the initial assessment when all Complete TMA Response criteria were met.

For laboratory data, in the event of duplicate samples from local and central laboratories (for any time point), central laboratory results will be used for analysis.

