15.12. Other Statistical Issues

15.12.1. Missing or Invalid Data

If a Day 1 assessment is missing, the Screening assessment will be used as the baseline assessment.

For evaluation of Complete TMA Response during the 26-week Initial Evaluation Period (primary endpoint), patients missing an efficacy assessment that is part of the definition of Complete TMA Response while still on-study, will have their last observation carried forward (LOCF). For patients who will have terminated early from the study prior to Week 26, their data up to the time of discontinuation will be used to assess Complete TMA Response.

Missing data for QoL instruments will be handled as specified in the instructions for each instrument.

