5. DEFINITIONS

5.1. Efficacy

5.1.1. Primary Endpoint(s)

The primary efficacy endpoint of the study is Complete TMA Response during the 26 week Initial Evaluation Period. The criteria for Complete TMA Response are the following:

1. Normalization of platelet count (defined as platelet count $\geq 150,000$ per microliter)
2. Normalization of LDH (defined as LDH \leq upper limit of normal)
3. $\geq 25\%$ improvement in serum creatinine from baseline

Patients must meet all Complete TMA Response criteria at 2 separate assessments obtained at least 4 weeks (28 days) apart, and any measurement in between.

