9.4.4. Analysis Visits

Summaries over postbaseline time points or analyses at specific postbaseline time points will be performed based on the list of visits described in the schedule of assessment of the protocol. For all assessments, the number of days from baseline will be calculated using the following formula: (date of assessment) - (date of first study treatment) + 1. This number of days will be used to assign analysis visit. This may not always correspond to the electronic case report form (eCRF) visit.

The analysis visit assignment for a specific assessment will be based on visit windows around each scheduled visit for that specific assessment. The windows for each scheduled visit will go from the midpoint (in days) between the current visit and the previous scheduled visit to the midpoint between the current visit and the subsequent scheduled visit. If the interval separating 2 scheduled visits is an even number of days, that middle day will be included in the later visit window and excluded from the prior visit window. For example, for an assessment with a scheduled visit Day 127, and a prior scheduled visit Day of 113 and subsequent scheduled visit Day of 141, the window will start at 120 days from baseline and will go to 133 days from baseline.

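### As worded, the SAP's carry-forward rule could let a value carried from a later qualifying visit confirm a 28-day Complete TMA Response on only 14 observed days

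*SAP*

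**What the plan says.** SAP 5.1.1 and 7.2.1 define a responder as a patient who meets the platelet, LDH and creatinine criteria "at 2 separate assessments obtained at least 4 weeks (28 days) apart, and any measurement in between". SAP 7.2.1 adds that "the latest time point a patient can first meet the response criteria is 28 days before the Day 183 assessment", which is nominally Day 155.

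Protocol 15.12.1 applies last observation carried forward to "patients missing an efficacy assessment that is part of the definition of Complete TMA Response while still on-study" and sets no limit on it. SAP 7.2.1.1 repeats that rule and adds one restriction: "A confirmatory result cannot be from an assessment that was carried forward from the initial assessment when all Complete TMA Response criteria were met". Neither document limits the number of consecutive visits that may be filled. Nothing is carried past study discontinuation; for those patients "their data up to the time of discontinuation will be used to assess Complete TMA Response".

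The planned sensitivity analysis of the primary endpoint (SAP 7.2.1.5) is a repeat on the Per Protocol Set.

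**The concern.** The 28-day confirmation separates a sustained response from a short fluctuation. The SAP's restriction names one source only, the initial qualifying assessment. On a 14-day visit schedule another visit normally lies between the initial visit and the one 28 days later. If that middle visit also qualifies, its values can be carried into an empty 28-day visit without breaking the restriction. The patient would then be scored as confirmed on 14 observed days, even if the next real measurement shows failure.

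Allowing a carried value to confirm can add responders and cannot remove any. The study has one arm, and SAP 7.2.1 says its rate will be set beside results from prospective eculizumab studies, so an error in one direction matters more than it would in a randomized comparison.

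**Working it through.** **The plan's own precision figure.** Inputs: response rate 0.65 and n = 50 (SAP 9.3); normal-approximation interval with continuity correction (SAP 7.2.1). Half-width = 1.96 × √(0.65 × 0.35 / 50) + 1/(2 × 50) = 0.1322 + 0.0100 = 0.1422. This agrees with the stated figure of about 15%. The present point does not affect it; it serves as a scale.

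**Visit days.** Protocol Table 1 schedules chemistry and hematology on Days 8, 15, 22 and 29, then every 14 days to Day 183. SAP 9.4.4 shows the same spacing in its example, "with a scheduled visit Day 127, and a prior scheduled visit Day of 113 and subsequent scheduled visit Day of 141".

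**Applying the rules.** Each pattern assumes that the patient stays on-study, that visits not listed fail, and that intervals are counted on scheduled days.

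| Pattern | SAP 7.2.1.1 as worded | Protocol 15.12.1 as worded | Confirmation must be observed |
|---|---|---|---|
| 57 and 71 met, 85 missing, 99 fails | responder | responder | non-responder |
| 155 and 169 met, 183 missing | responder | responder | non-responder |
| 57 met, 71 and 85 missing, 99 fails | non-responder | responder | non-responder |
| 57 and 71 met, 85 missing, 99 met | responder | responder | responder |
| 57 and 71 met, 85 fails | non-responder | non-responder | non-responder |

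In the first row, Day 85 takes the Day 71 values. Their source is not the initial assessment, and 85 − 57 = 28, yet the observed span is 71 − 57 = 14 days. In the second row, 183 − 155 = 28 and 169 − 155 = 14. The third row is the case the SAP's sentence does stop. The fourth shows that a good next visit makes the gap irrelevant.

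The first-row result recurs for every starting visit with scheduled visits 14 and 28 days later: Day 15 (Day 22 must also qualify) and Days 29 to 155, 11 starting visits in all.

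**The extreme case.** A 7-day observed span is possible only from the weekly visits. Days 8 and 15 met (15 − 8 = 7) need Days 22, 29 and 43 all missing. Starting on Day 15 or Day 22, two consecutive visits must be missing (29 and 43, or 43 and 57).

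**When a component counts as missing.** SAP 9.4.4 uses midpoint-to-midpoint windows. For Day 85 the midpoints are (71 + 85)/2 = 78 and (85 + 99)/2 = 92, so any result from Day 78 to Day 91 serves. For Day 183 they are (169 + 183)/2 = 176 and (183 + 239)/2 = 211, giving Days 176 to 210. Local results are used if no central result exists (SAP 5.2.3). A whole visit need not be lost, however. SAP 5.2.3, 9.4.9 and 9.4.10 remove LDH from hemolyzed samples, creatinine on dialysis and platelets after transfusion, and the SAP does not say whether a removed value is then filled by carry-forward.

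**Effect per patient.** 1/50 = 2.0 points; 1/55 = 1.8 points. The number of affected patients is not in the documents. As an assumed range only, starting from 32/50:

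| Patients reclassified | Rate | 95% CI |
|---|---|---|
| 0 | 64% | 49.7% to 78.3% |
| 1 | 62% | 47.5% to 76.5% |
| 2 | 60% | 45.4% to 74.6% |
| 3 | 58% | 43.3% to 72.7% |
| 5 | 54% | 39.2% to 68.8% |

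**Would the planned sensitivity analysis show it?** Per Protocol Set membership (SAP 6.2) depends on infusions, prohibited treatments and eligibility. Initial Evaluation Period doses fall on Days 1, 15, 71 and 127 (Protocol Table 6), so a missing Day 85 or Day 183 laboratory result does not by itself remove a patient. The same carried confirmation would pass into the repeat analysis.

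**The case against.** The strongest reply is that the endpoint definition already settles the matter. A Day 71 value carried to Day 85 was obtained on Day 71, 14 days after Day 57, so the two assessments were not obtained 28 days apart. This reading is legitimate, and a reader should not infer that such patients will certainly be counted as responders. But if no carried value could ever confirm, the SAP's restriction would be unnecessary. Barring one source suggests that others are allowed. The two passages point in different directions, and the programmer would have to choose.

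The second reply is that the situation should be uncommon. The windows are wide, unscheduled visits are permitted (Protocol 7.3), local results serve as back-up, and nothing is carried after discontinuation. This stands, and it limits how many patients could be affected. It does not remove the ambiguity.

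Three stronger inferences are tempting and are not supported. One is that the reported rate would be inflated by a particular number of points: the documents give no rate of missing results. Another is that deteriorating patients are more likely to miss visits: nothing in the documents shows this, and patients who receive plasma exchange or infusion or another complement inhibitor are withdrawn (Protocol 9.7), after which only their data to that time are used. The third is that 7-day responses would be credited routinely: that needs two or three consecutive empty visits early in the study.

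**Conclusion.** The concern holds as a gap in wording. SAP 7.2.1.1 could allow a Complete TMA Response to be confirmed on 14 observed days, in conflict with the 28-day requirement in SAP 5.1.1, and no planned analysis would expose it.

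The primary result changes only when all of these hold: the patient is on-study at the missed visit; no usable result for at least one component falls in that window; the next observed visit fails, or the missed visit is Day 183; and the patient has no other genuine 28-day run in the 26 weeks. Each such patient moves the rate by 2.0 points at n = 50 or 1.8 points at n = 55, against a planned half-width of about 15 points. The conclusion rests on a literal reading of the restriction and on scheduled rather than actual visit days. It should be corrected, because it bears on responder status for the primary endpoint and can err only upward.

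**What to change.** Replace the last sentence of the first paragraph of SAP 7.2.1.1 with:

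> The confirmatory result must be based on observed (not carried-forward) platelet count, LDH and serum creatinine, obtained at least 28 days after the initial assessment at which all criteria were met; LOCF may be used only for visits in between. If the 28-day visit is missing, the next observed visit within the Initial Evaluation Period may confirm.

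Record the change in SAP 4.1, which now declares no departures from the protocol, because it narrows the rule in Protocol 15.12.1. Report the primary rate under the present carry-forward rule as a sensitivity analysis, so that any difference is visible.

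Visits, sample size and patient care are unchanged. The cost is that a true responder with no usable Day 183 result may go unconfirmed, as in the Days 155 and 169 example, where nothing shows a relapse. The new sentence also means that a visit with a carried component cannot serve as the initial assessment, so the start of the run moves to the next fully observed visit. The reported rate may therefore be slightly lower.

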7.2.1.2. Subgroup Analysis

The primary efficacy analysis will be repeated separately by the following subgroups:

- gender (male, female)
- race
- ethnicity
- geographic region (by country)
- age at enrollment categories (12-17, 18 years of age and up)
- kidney transplant history (yes, no)
- immunogenicity status (ever positive, always negative)
- dialysis within 5 days prior to treatment initiation (yes, no)
- met all laboratory criteria for TMA as determined by the central laboratory at Day 1

Given that the number of patients in these subgroups may be limited, the CIs will be based on exact confidence limits using the Clopper-Pearson method. For the same reason, some subgroup categories may be combined.

7.2.1.3. Multicenter Studies

The number of patients at each center is expected to be very small. Therefore, there will be no summarization of efficacy analyses by site.

7.2.1.4. Hypothesis Testing and Significance Level

This is an estimation study and no formal statistical tests are planned. The primary efficacy endpoint will be analyzed using an asymptotic 95% 2-sided confidence interval for the proportion of complete TMA responders.

7.2.1.5. Sensitivity Analyses

The primary and selected secondary efficacy endpoints will be analyzed based on the on the PPS to determine if the results are materially different from the analysis based on the FAS.

7.2.2. Secondary Analyses

Secondary Analyses will be performed on the FAS. Separate by-patient listings will be created for all secondary efficacy analysis parameters.

Continuous variables will be summarized using descriptive statistics, including number of observations and mean, standard deviation, median, minimum, and maximum values. Categorical variables will be summarized by frequency counts and percentage of patients.

7.2.2.1. Dialysis Requirement Status

An analysis will present the number and proportion of patients that are requiring dialysis over time. A 2-sided 95% CI for the proportion will be provided. The CI will be based on exact confidence limits using the Clopper-Pearson method. The summary will be produced for patients requiring dialysis within 5 days prior to ALXN1210 treatment initiation, not requiring dialysis within 5 days prior to ALXN1210 treatment initiation, and overall. A patient will be considered as not requiring dialysis at a specific postbaseline time point if they have been dialysis free for at least 5 days prior to that time point. A by-patient figure showing dialysis status or events over time will be presented.

7.2.2.2. Time to Complete TMA Response

For the secondary efficacy endpoint of time to Complete TMA Response, Kaplan Meier cumulative distribution curves will be generated along with 2-sided 95% CIs. The corresponding summary table will present the cumulative distribution function (CDF) estimate, the number of patients at risk, the number of patients responding, and the number of patients censored at each postbaseline time point. The table will also present first quartile, median, and third quartile, along with corresponding 2-sided 95% CI, of time to complete response.

Complete TMA response is defined in [Section 5.1.1](#). Patients must meet all Complete TMA Response criteria at two separate assessments obtained at least 4 weeks (28 days) apart, and any measurement in between. The time of the event of a confirmed complete TMA response will be considered as the first time point at which all the criteria for complete TMA response were met.

Patients that did not have a response will be censored at the date of last visit or study discontinuation at the time when the analysis is performed.

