- ^p Urine sample for drug measurement will be collected at end of infusion (EOI) (within 0.5 hours after the EOI) on Days 1, 15, and 71; and at any time on Day 29.
- ^q Collection will be predose.
- ^r A single whole blood collection from those patients who consent to genetic testing can be collected anytime during the study.
- ^s ADA serum samples will be collected predose on Days 1, 71, and 127. Day 183 collection will occur prior to first dose in the Extension Period. Early termination collection will occur at any time on the ET visit day. All collection times will be recorded in the eCRF.
- ^t Review the Clinical Trial Participant Safety Information Card with the patient and discuss the importance of carrying the safety card at all times, and the risks ALXN1210 treatment, including the risk of meningococcal infection.
- ^u Concomitant medications must be collected at all study visits and checked against the prohibited medication listed in [Section 9.7](#).

Table 1: Schedule of Study Visits and Assessments: Screening Through End of Initial Evaluation Period (Continued)

^v The dose of ALXN1210 is based on the patient's last recorded study visit body weight (Day 1 dosing is based on the body weight at Screening).

^w If a local laboratory is used to define eligibility, additional samples will be collected during the Screening Period for LDH, platelet count, hemoglobin and serum creatinine and tested at the central laboratory.

^x The primary efficacy endpoint assessment is before dosing on Day 183. Dosing on Day 183 is the start of the Extension Period. Please refer to additional Day 183 postdose assessments in [Table 2](#).

Table 2: Schedule of Study Visits and Assessments: Extension Period Day 183 to Day 911

Period	Extension Period													
	183 ^p	239	295	351	407	463	519	575	631	687	743	799	855	911
Study Day	±2	±7	±7	±7	±7	±7	±7	±7	±7	±7	±7	±7	±7	±7
Window (day)	±2	±7	±7	±7	±7	±7	±7	±7	±7	±7	±7	±7	±7	±7
Weight		X	X	X	X	X	X	X	X	X	X	X	X	X
Pregnancy test ^a	X	X	X	X	X	X	X	X	X	X	X	X	X	X
FACIT-Fatigue questionnaire /Pediatric FACIT-Fatigue questionnaire ^{b,c}				X				X			X			X
EQ-5D-3L questionnaire ^c				X				X			X			X
Patient-reported aHUS symptoms questionnaire ^c		X	X	X	X	X	X	X	X	X	X	X	X	X
Resource utilization patient questionnaire ^c		X	X	X	X	X	X	X	X	X	X	X	X	X
Abbreviated physical examination ^d		X	X	X	X	X	X	X	X	X	X	X	X	X
Assessment of extra-renal signs or symptoms of aHUS		X	X	X	X	X	X	X	X	X	X	X	X	X
Vital signs ^e		X	X	X	X	X	X	X	X	X	X	X	X	X

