7.2.2.3. Complete TMA Response Status Over Time and Alternative Definitions

Complete TMA Response will also be summarized over time by presenting the number and proportion of responders along with a 2-sided 95% CI for each postbaseline time point. This summary will be accompanied by a similar presentation for the components of complete TMA response: proportion of patients with platelet count normalization, proportion of patients with LDH normalization, proportion of patients with hematologic normalization (platelet count and LDH), proportion of patients with $\geq 25\%$ improvement in serum creatinine from baseline. The CIs will be based on the asymptotic Gaussian approximation method with a continuity correction. These tabular summaries will be accompanied by a bar chart graphical figure displaying for each time point a bar for Complete TMA Response and each component in its definition, where the bar will represent the proportion of patients meeting that specific criterion.

A patient will be included in the analysis for a specific postbaseline time point if it was possible for the result at that time point to be confirmed or to serve as a confirmatory result.

A set of summaries similar to the ones described above will be produced without any requirement for a confirmatory result. This summary will be strictly based on a patient meeting the criterion at a specific time point.

A slightly modified version of complete TMA response will also be evaluated. The modification will only affect patients considered to be on dialysis at baseline (ie. patients requiring dialysis within 5 days prior to ALXN1210 treatment initiation). For these patients, the criterion requiring

an improvement from baseline of 25% or more in serum creatinine, will be replaced by a postbaseline change in dialysis status (from requiring dialysis at baseline to no longer requiring dialysis) that is maintained for at least 4 weeks. A set of summaries similar to the ones described above will be produced based on this alternative definition.

The tabular summary of complete TMA response over time will also be performed on the PPS.

7.2.2.4. eGFR Value and Change from Baseline

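### Time to Complete TMA Response: non-responders stay at risk over a final stretch in which no response can count, so the Kaplan-Meier curve reads modestly low, mainly after Day 155

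*SAP*

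**What the plan says.** - **What counts.** SAP 5.1.1 requires all criteria to be met "at 2 separate assessments obtained at least 4 weeks (28 days) apart, and any measurement in between". SAP 7.2.2.2 repeats this for the time-to-response analysis.
- **Event time.** Under SAP 7.2.2.2 the time of a confirmed response "will be considered as the first time point at which all the criteria for complete TMA response were met".
- **Censoring time.** The same section says: "Patients that did not have a response will be censored at the date of last visit or study discontinuation", as of when the analysis is run. It makes no allowance for the confirmation interval. Protocol 15.8.2.2 describes the Kaplan-Meier analysis but gives no censoring rule.
- **Confirmation cannot be borrowed.** SAP 7.2.1.1 says: "A confirmatory result cannot be from an assessment that was carried forward from the initial assessment". For early leavers, "their data up to the time of discontinuation will be used to assess Complete TMA Response".
- **The principle appears elsewhere.** For the primary analysis, SAP 7.2.1 states that "the latest time point a patient can first meet the response criteria is 28 days before the Day 183 assessment". For hemoglobin response, SAP 7.2.2.7 keeps a patient in a time point's summary only if the patient stays in the study for a confirmatory assessment at least 28 days later.
- **Extension visits.** The Protocol 7.3 table titled "Schedule of Study Visits and Assessments: Extension Period Day 183 to Day 911" places visits at Days 183, 239, 295, 351 and so on, 56 days apart.

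**The concern.** The analysis runs on two clocks. Events are placed at the first qualifying visit, but they exist only if follow-up continues for another 28 days. Censoring is placed at the very end of follow-up. Every non-responder's record therefore closes with a stretch in which the patient sits in the denominator but cannot enter the numerator.

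For example, a patient last seen on Day 183 who first meets all criteria on Day 169 cannot be confirmed in that analysis, and is scored as event-free and at risk through Day 183. Uninformative drop-out does not cure this, because the problem lies in the rule and not in who leaves.

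Time to response is a named secondary endpoint. SAP 7.2.2.2 asks for the estimated curve and the number at risk at each time point. SAP 7.2.1.4 calls this an estimation study without formal tests, and SAP 7.2.1 says results will be read beside earlier eculizumab studies. An accurate curve is therefore what the analysis is for, and a downward bias cannot be excused as conservative.

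**Working it through.** **1. The plan's own cut-off.** 183 − 28 = Day 155, the last first-met time that can count in the Initial Evaluation Period. The documents give no other figure for this analysis.

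**2. Last confirmable visit on the protocol schedule.** For last visit C, the last confirmable visit L is the latest scheduled visit no later than C − 28.

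| Last visit C | Last confirmable L | Gap (days) | Visits at risk with no countable event |
|---|---|---|---|
| 99 | 71 | 28 | 85, 99 |
| 183 | 155 | 28 | 169, 183 |
| 239 | 183 | 56 | 239 |
| 911 | 855 | 56 | 911 |

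**3. Direction.** At visit v the Kaplan-Meier step is d(v)/n(v). A first-met response at v enters d(v) only if L ≥ v. Under the SAP rule a non-responder enters n(v) whenever C ≥ v. Non-responders with L < v ≤ C enlarge n(v) and can never add to d(v), so each affected step is too small. If everyone reaches Day 183, L is at least 155 for all, and the curve is unaffected up to Day 155.

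**4. Data cut at Day 183, no early leavers.** With 65% confirmed by Day 155, 55 × (1 − 0.65) = 19.25. About 19 patients would be tabulated as at risk on Days 169 and 183 with d = 0 by rule, so the curve is flat after Day 155.

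**5. Size.**

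Inputs from the SAP (9.3): 65% response and 10% drop-out.

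Assumptions not in the documents: exponential response times with a long-run ceiling π, sustained responses, independent exponential drop-out, visits on schedule, and extra follow-up uniform on 0 to 365 days after Day 183 at the first analysis.

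Model: F(t) = π(1 − exp(−λt)), with λ = −ln(1 − 0.65/π)/155, so that F(155) = 65%. For π = 80%, λ = −ln(0.1875)/155 = 0.0108 and F(183) = 0.80 × (1 − exp(−0.0108 × 183)) = 68.9%.

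Simulated results, 100,000 patients per ceiling, 10% drop-out by Day 183:

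| Ceiling π | Day | True % | SAP rule % | Proposed rule % | Shortfall (true − SAP) |
|---|---|---|---|---|---|
| 70% | 155 | 64.9 | 64.2 | 64.8 | 0.7 |
| 70% | 183 | 66.8 | 65.8 | 66.8 | 1.0 |
| 70% | 351 | 69.8 | 68.2 | 69.9 | 1.6 |
| 80% | 155 | 65.0 | 64.2 | 64.9 | 0.8 |
| 80% | 183 | 68.9 | 67.5 | 68.8 | 1.4 |
| 80% | 351 | 78.1 | 75.1 | 78.1 | 3.0 |
| 100% | 155 | 65.1 | 64.4 | 65.1 | 0.7 |
| 100% | 183 | 71.3 | 69.6 | 71.3 | 1.7 |
| 100% | 351 | 90.7 | 86.4 | 90.7 | 4.3 |

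A ceiling of 90% gives shortfalls of about 1.5 (Day 183) and 4.0 (Day 351). The range for ceilings of 70% to 90% is therefore about 1.0 to 1.5 and 1.6 to 4.0. The 100% rows are the extreme case in which everyone eventually responds.

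Other scenarios:
- Initial Evaluation Period only, Day 155: shortfall 0 with no drop-out, 0.6 to 0.8 with 10%, about 1.5 with 20%.
- Data cut at Day 183, 10% drop-out, π = 80%: the SAP curve stays at 64.6% while the truth at Day 183 is 69.2%. The proposed rule gives 65.3% at Day 155 (true 65.2%) and no estimate beyond.
- Final analysis, with an assumed 0 to 1,680 days of follow-up after Day 183: Day 351 shortfalls of 69.8 − 68.9 = 0.9, 78.1 − 77.0 = 1.1 and 90.6 − 89.4 = 1.2 points for ceilings of 70%, 80% and 100%.

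**6. Scale.** The sampling SD of a 65% proportion in 55 patients is √(0.65 × 0.35/55) = 6.4 points, so 0.7 points is small beside it.

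**The case against.** The strongest reply is that little turns on this. There are no formal tests, and the primary endpoint is a proportion of the FAS that this rule does not touch. The numbers censored are tabulated, and SAP 7.2.2.3 also plans by-visit summaries without confirmation. In a separate simulation at the planning values with 55 patients, the two censoring rules gave the same median in 82% to 89% of trials and the same first quartile in 94% to 97%. All of this stands, and it limits the size of the point. It does not make the rule right.

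The documents do not support several stronger readings that a reader might infer:

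- **That late responses can never be counted.** This holds only within one analysis. SAP 4.3 plans a second analysis, by which a response unconfirmed at the first can have been confirmed.
- **That 56 days are always lost in the Extension Period.** That gap follows from the visit schedule. Protocol 7.3 permits unscheduled visits, so the hard limit is 28 days.
- **That SAP 7.2.2.3 already restricts the by-visit table to confirmable results.** It admits a patient "if it was possible for the result at that time point to be confirmed or to serve as a confirmatory result", so a result that can only confirm an earlier one also qualifies. SAP 7.2.1 and 7.2.2.7 are the better precedents.
- **That the curve will be flat from Day 155.** This depends on cutting data at Day 183, which SAP 7.2.2.2 does not state.
- **That the quartiles and confidence intervals are materially wrong.** No such effect has been shown. The effect on the confidence intervals has not been quantified.

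A fair criticism of any remedy is that it must say which later assessments qualify. The wording proposed below does so for carried-forward values.

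**Conclusion.** The censoring rule in SAP 7.2.2.2 is wrong as written, with modest impact, and nothing else in either document corrects it. The direction follows from the rules alone: the curve is too low wherever some follow-up ends inside the confirmation interval.

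The size depends on the assumed response-time model and follow-up. At the planned response and drop-out rates it is about 0.7 points up to Day 155, and that part comes only from early leavers, so the first quartile and median should move little. The main effect lies after Day 155: about 1.0 to 1.5 points at Day 183 and 1.6 to 4.0 at Day 351 at a first analysis with up to a year of extra follow-up. It is smaller with the longer follow-up of a final analysis. A Day 183 data cut would give a tail that looks as if responses had stopped, with patients still listed at risk.

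**What to change.** In SAP 7.2.2.2, replace the censoring sentence with wording such as: *Patients without a confirmed response will be censored at their last assessment that has a later assessment of the response criteria at least 28 days afterwards (Day 1 if none). A value carried forward from the initial assessment does not count as the later assessment. The number at risk will be based on this time.*

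This agrees with the cut-off in SAP 7.2.1, the carry-forward rule in 7.2.1.1 and the hemoglobin rule in 7.2.2.7. In the simulations it brought the curve to within about 0.2 points of the truth wherever it could be estimated. The SAP should also say whether an assessment whose creatinine is excluded for dialysis (SAP 9.4.9) counts as an assessment of the criteria.

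The cost is one SAP sentence and a small programming change, smaller late risk sets, slightly wider late confidence intervals, and no estimate beyond Day 155 if data are cut at Day 183.
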